### 11. SECONDARY AIMS

The **secondary aims** are to determine the effectiveness of HWC in improving

1. Overall cardiovascular disease (including stroke) risk at 6 months post-randomisation based on the LS7 compared to Baseline

2. Individual LS7 behavioural risk factors at 3-, 6- 9- and 12- months post-randomisation compared to Baseline
3. Awareness about stroke symptoms, risk factors and their management 6- and 12- months post-randomisation compared to Baseline
4. Quality of life, at 6- and 12- months post-randomisation compared to Baseline
5. Cognitive outcomes at 6-, and 12- months post-randomisation compared to Baseline
6. Mood outcomes compared to Baseline
7. Adherence to CVD medications at 3, 6-, and 9 and 12- months compared to Baseline
8. CVD/adverse outcomes at 12 months post randomisation.
9. Health and service costs at 12 months post randomisation
10. Productivity status at 12 months post randomisation

Secondary outcomes are:

1. systolic blood pressure, total cholesterol, blood glucose at 6-months post randomisation
2. change in proportion of participants in 'high' and 'intermediate' to 'low' risk on LS7 at 6-months post randomisation
3. Stroke risk from Stroke Riskometer – 5- year absolute and relative risk at 6- and 12-months post randomisation
4. Quality of life (EQ5D) at 6-months post randomisation
5. Stroke awareness at 6- and 12-months post randomisation
6. Cognitive assessment score (Montreal Cognitive Assessment)
7. Medication adherence (Self-Efficacy For Appropriate Medication Use Scale (SEAMS))
8. CVD adverse outcomes (fatal and nonfatal stroke, TIA, myocardial infarction and heart failure, death attributable to CVD and all-cause mortality)
9. Healthcare and community service costs assessed as self-reported service use questionnaire at follow up. Productivity status will be self-reported and will include items regarding status (e.g., paid work, voluntary work, homemaker, student, unemployed), hours (e.g., full/part time), compared to hospitalisation pre-stroke status.

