### 3.5 CASE RECORD FORMS AND QUESTIONNAIRES

#### 20. LIST OF QUESTIONNAIRES

Table 1. List of outcome measures

Outcome measure	Baseline	3	6	12
Demographic Factors: Age, sex, ethnicity, employment, education, marital status	✓			
Event type - stroke and pathological subtypes, or TIA and event date (physician diagnosed)	✓			
Hospitalization details: hospital, date of admission, date of discharge	✓			
Event details (revascularization and planned procedures) from medical records	✓			
Hospital Anxiety and Depression Scale	✓	✓	✓	✓
Stroke awareness (recognition of risk factors, knowledge of actions) [61]	✓	✓	✓	✓
Quality of life (EQ-5D-5L) [62]	✓		✓	
Cognitive functioning by MoCA [63]	✓		✓	
Medication adherence and self-efficacy (SEAMS) REF)	✓	✓	✓	✓
Physical measurements (non-fasting blood test, SBP/DBP, BMI, HR)*	✓		✓	
Absolute and relative 5-year risk of stroke (as measured by Stroke Riskometer app)	✓		✓	
Lifestyle factors (Diet score, physical activity, smoking, alcohol)	✓	✓	✓	✓
CVD outcomes, recurrent events, hospitalisation (stroke, CVD events) self-report and/or from clinical records	✓	✓	✓	✓
Health and Service costs: NMDS (NZ)			✓	✓
Productivity level NMDS (NZ)	✓	✓	✓	✓
Participant feedback questionnaire – Intervention group only	✓	✓	✓	✓

Items will include demographic factors, medical history, lifestyle risk factors, awareness of stroke risk factors, warning signs, symptoms and actions;[64] depression screening test (Hospital Anxiety and Depression Scale) health related quality of life ([EQ-5D-5L](#)),[62] health-care resource

use questionnaire, cognitive assessment (Montreal Cognitive Assessment MoCA) and participant satisfaction questionnaires. See 2 for details of measures collected at each timepoint. Life's Simple 7 score will be calculated from corresponding measurements of smoking, BMI, physical activity, healthy diet score, blood total cholesterol, glucose level and BP.[37]

Table 2. Life's Simple 7

Modifiable factors	Poor health	Intermediate health	Ideal health
Smoking status	Current smoker	Former ≤ 12 months	Never or quit > 12 months
Body mass index	≥ 30 kg/m 	25–29.9 kg/m 	< 25 kg/m 
Physical activity	No physical activity	1–3 times, less than 2.5 hours per week	≥ 4 times per week, 2.5 hours or more
Healthy diet score	0–1 component	2–3 components	4–5 components
Total cholesterol	≥ 240 mg/dL	200–239 mg/dL or treated to goal	< 200 mg/dL

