## 29. OUTCOME ASSESSMENTS (SEE TABLE 1 FOR THE FULL LIST OF OUTCOMES)

**Baseline:** The baseline assessment will be conducted prior to randomisation, and within 6 weeks of the index event. The Baseline assessment will be conducted in-person. The initial part of the assessment will be used to determine the full eligibility of the participant for the TIIPS trial. The full assessment will be completed for eligible participants only, and will include all measures required to analyse the primary and secondary outcomes

**3 months** (plus or minus 2 weeks from date of randomisation): The assessment will be conducted by telephone only, and will assess secondary outcomes.

**6 months** (primary outcome) (plus or minus 2 weeks from date of randomisation): The 6- month assessment be conducted in-person and will re-assess the primary outcome as well as secondary outcomes.

**9 months** (plus or minus 2 weeks from date of randomisation): The assessment will be conducted by telephone only, and will assess secondary outcomes.

**12 months** (plus or minus 2 weeks from date of randomisation): The assessment will be conducted by telephone only, and will assess secondary outcomes.

---

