### 34. INFERENCE ANALYSES

Intention to treat (ITT)[95] analyses and per protocol analysis will be used. To address the primary hypothesis ANCOVA will be used to compare the difference in systolic blood pressure at 6-months post randomisation between the HWC and usual care groups, accounting for baseline stratification factors: (age, gender and ethnicity), referral centres, geographical region and known influential clinical characteristics (e.g., comorbidities). To address the secondary hypotheses linear mixed effects (LME) repeated measures models will be used to investigate the differences in (1) adherence to medication (2) health-related quality of life (3) incidence of new vascular events including death (4) life satisfaction (5) cognition (6) mood) and (7) health service utilisation costs between the HWC and Usual care groups, and by ethnicity (sub-group analysis) at 6-months (plus

life-style and adherence at 1-year post-randomisation. These LMEs will model effect of time (baseline, 3-, 6- 9- and 12-months (medication adherence, lifestyle and awareness at only 12 months), post-randomisation whilst accounting for key demographic stratification factors known to confound with outcomes. Any data not collected within 6-weeks of the follow-up points will be classified as missing data. Baseline covariates of age, sex, most recent blood pressure measure and any additional variables predictive of outcome data will be included in the imputation model.[46] The reasons for missingness and the reasons will be recorded and accounted for. Sensitivity analyses will be conducted to test the assumptions of the model (including a complete case analysis in which only subjects with complete data are included). Familywise error control will be used to account for the multiplicity of tests. Inferences will be based on a 5% significance level and two-sided alternatives.

For the analysis of - CVD adverse outcomes (fatal and nonfatal stroke, TIA, myocardial infarction and heart failure, death attributable to CVD and all-cause mortality), we will use Kaplan-Meier life-test and estimate the hazard ratios (HR) and adjusted HR using time-to-event Cox regression analysis. Time to event analysis will include recurrent events and time-dependant variables where appropriate.

Competing risk method will also be applied to compare the CVD adverse outcomes between the two interventional groups, accounting for mortality outcome.

---

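### Secondary mixed models treat baseline as an ordinary time level, with no common-baseline constraint or baseline-score covariate, so the arm contrasts can be valid but needlessly imprecise

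*Protocol*

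**What the plan says.** Section 34 assigns the secondary outcomes to linear mixed-effects repeated-measures models. Of these it says "These LMEs will model effect of time (baseline, 3-, 6- 9- and 12-months", followed by a parenthesis limiting some outcomes to certain visits. Adjustment is described as "whilst accounting for key demographic stratification factors known to confound with outcomes". The comparison of interest is "between the HWC and Usual care groups, and by ethnicity (sub-group analysis) at 6-months (plus", with lifestyle and adherence added at one year.

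The same paragraph names other baseline variables, but for a different purpose: "Baseline covariates of age, sex, most recent blood pressure measure and any additional variables predictive of outcome data will be included in the imputation model". No sentence puts the baseline value of the outcome into the mixed model, requires the two arms to share a baseline mean, names an arm-by-time term, or says which contrast estimates the arm effect.

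Two other places matter. Section 29 fixes the timing: "The baseline assessment will be conducted prior to randomisation, and within 6 weeks of the index event". Section 11 frames several secondary aims as change from baseline, for example "Quality of life, at 6- and 12- months post-randomisation compared to Baseline".

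**The concern.** The baseline score is measured before allocation, so the arms have the same expected mean there and differ only by chance. A model that gives each arm its own baseline mean ignores that fact. If the arm effect is then read as change from baseline, as the Section 11 aims suggest, the full baseline noise is subtracted from the follow-up value. If it is read as the plain 6-month difference, the baseline score does nothing to reduce the noise. In both cases the contrast is unbiased, but it is less precise than the same data allow.

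The outcomes concerned are those on the Section 34 mixed-model list that have a baseline score: medication adherence (SEAMS), quality of life (EQ-5D-5L), life satisfaction (on the baseline and follow-up case record forms), cognition (MoCA) and mood (HADS). At stake are interval width and power for these secondary comparisons. The primary ANCOVA of systolic blood pressure is outside this point.

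**Working it through.** The protocol gives no variance, correlation or power for any secondary mixed model, so it has no figure to reproduce.

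**Inputs.** 1:1 allocation (Randomisation section); baseline before randomisation (Section 29). Assumed: equal variances over visits, compound symmetry, complete data, and a correlation rho between baseline and follow-up of 0.4 to 0.8.

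**Variances of the 6-month arm effect**, in units of 2σ²/n with n per arm:
- arms free at baseline, change-from-baseline contrast: 2(1−rho)
- arms free at baseline, plain 6-month difference: 1
- common baseline mean: 1−rho²

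**Ratios to the common-baseline model:**
- change contrast: 2(1−rho)/[(1−rho)(1+rho)] = 2/(1+rho)
- plain 6-month difference: 1/(1−rho²)

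| rho | change contrast | plain 6-month difference |
|---|---|---|
| 0.4 | 1.43 | 1.19 |
| 0.5 | 1.33 | 1.33 |
| 0.6 | 1.25 | 1.56 |
| 0.7 | 1.18 | 1.96 |
| 0.8 | 1.11 | 2.78 |

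Exact generalised least squares calculations gave these ratios for visit sets 0/6, 0/3/6/12 and 0/3/6/9/12 months. Under these assumptions the result therefore does not depend on which of these schedules applies.

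**What this means for the change contrast.** The efficiency lost is 1 − (1+rho)/2 = (1−rho)/2. That is equivalent to discarding 30% of participants at rho 0.4, 15% at 0.7 and 10% at 0.8. Intervals are wider by √1.43 = 1.20 at rho 0.4 and √1.11 = 1.05 at rho 0.8.

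**A rough document-based correlation.** Section 6 gives Life's Simple 7 results from the sponsor's previous coaching trial: 7.08 (SD 2.03) to 7.39 (2.00) with coaching, 7.15 (2.20) to 7.15 (2.39) in controls, p=0.044.
- The difference in change is 0.31. With z = 2.014 the standard error is 0.31/2.014 = 0.154.
- With n=320, the variance of change is 0.154² × 320/4 ≈ 1.90.
- The mean sum of the two variances is (2.03² + 2.20² + 2.00² + 2.39²)/2 = 9.34, so the covariance is (9.34 − 1.90)/2 = 3.72.
- The mean product of SDs is (2.03×2.00 + 2.20×2.39)/2 = 4.66, so rho ≈ 3.72/4.66 = 0.80.
- With n=251 (the number in Section 7), rho ≈ 0.84. If p=0.044 came from an ANCOVA, rho is about 0.78 to 0.83.

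These values give 9% to 12% excess variance for the change contrast. The Life's Simple 7 total is not on the Section 34 mixed-model list, so this is only a rough guide.

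**Pooled arm coefficient, for comparison only.** If one arm effect were averaged over all visits including baseline, a constant post-baseline effect would be recovered in the proportion of visits after baseline: 1/2 for 0/6, 3/4 for 0/3/6/12, 4/5 for 0/3/6/9/12.

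**The case against.** The strongest reply is that Section 34 does not commit to the weaker model. A common-baseline model is also set up with baseline as a level of time. The constraint, the arm-by-time term, the covariance structure and the contrast are details that a protocol often leaves to a statistical analysis plan, and none is shown here. This stands: the wording permits the inefficient model but does not force it, and the absence of that detail alone is no fault. What remains is that the structure as written lists baseline among the response times and names only demographic adjustment. An analyst following it literally would not reach the efficient version.

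A reader might also infer that the secondary effects are biased towards zero, with half the EQ-5D-5L or MoCA effect lost. The documents do not support that. Dilution needs a single arm coefficient pooled over baseline and follow-up, and Section 34 states its target as the arm difference at 6 months. The fraction is not settled either: Table 1 shows EQ-5D-5L and MoCA at baseline and 6 months only, while Section 11 also places quality of life and cognition at 12 months, which would make it two thirds.

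Nor does the point reach every outcome on the mixed-model list. Table 1 gives costs no baseline measurement. Incident vascular events have no comparable pre-randomisation value, and Section 34 also assigns them time-to-event methods.

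Finally, any single percentage depends on an assumed correlation, and the one value recoverable from the protocol points to the low end for the change contrast. That is also fair.

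**Conclusion.** The point holds as an avoidable loss of efficiency in secondary outcomes that have a baseline score. It is not a bias and does not touch the primary analysis. Against a common-baseline model, the change-from-baseline contrast carries 11% more variance at rho 0.8, 18% at 0.7 and 43% at 0.4. The plain 6-month difference carries 19% more at 0.4 and 96% more at 0.7.

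These figures rest on compound symmetry, equal variances, complete data and an assumed rho. They are approximate for MoCA and HADS, whose baseline distributions are truncated by the eligibility cut-offs. Correcting the wording is a free improvement rather than the repair of a demonstrated error.

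**What to change.** Reword the mixed-model sentence in Section 34, or settle it in the statistical analysis plan. For secondary outcomes with a baseline score, choose one of two forms:
- an arm-by-time model in which both arms share one baseline mean, so that arm terms appear only at post-baseline visits; or
- the baseline score as a covariate, with only post-baseline visits as response.

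Then state that the reported effect is the arm contrast at the visit named in each aim. For quality of life and cognition, Section 11 and Table 1 must first be reconciled on whether there is a 12-month measurement. Costs and incident events should be left out of this sentence.

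The cost is a sentence or two of text. The baseline scores are already collected, and no extra participants, visits or data are needed.

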## 35. INTERIM ANALYSES

The need for interim analysis will be the trial SC based on the recruitment rate or if advised by the independent DSMC using stopping guidelines for an effectiveness trial.[96]

## SERIOUS ADVERSE EVENTS

All hospitalisations (for any reason) are classified as Serious Adverse Events (SAEs), whether or not they are considered related to the health coaching intervention and should be reported to TIIPS study Manager or PI by the Research Assistant as soon as possible by completing a serious adverse event form (Appendix C Form S). If a participant is admitted to hospital, they should notify hospital staff that they are in the TIIPS trial. As this is an open label trial, clinical management should continue as usual.

All serious adverse events will be reported regularly to the Data Safety Monitoring Committee (see below). If at any time the DSMC considers there to be definite evidence of an excess of SAEs they will notify the TIIPS Trial Steering Committee of the findings. The Steering Committee will discuss the issues arising and determine the action to be taken. Copies of the reports issued by the DSMC will be available to Coordinating Centre staff.

An adverse event (AE) is any symptom, sign, illness or experience that develops or worsens in severity during the course of the study. Inter-current illnesses or injuries should be regarded as adverse events. Abnormal results of diagnostic procedures are considered to be adverse events if the abnormality:

- results in study withdrawal
- is associated with a serious adverse event
- is associated with clinical signs or symptoms
- leads to additional treatment or to further diagnostic tests
- is considered by the investigator to be of clinical significance

All adverse events that do not meet any of the criteria for serious should be regarded as non-serious adverse events.

## DATA SAFETY MANAGEMENT COMMITTEE

An independent Data Safety Monitoring Committee (DSMC) will be established to oversee the overall conduct of the study and ensure the safety of the trial and review of all serious adverse events (SAEs). SAEs will include all hospitalisation, new stroke, heart attack, death, and significant mood issues. Given the low-risk (non-pharmacological, no medical procedures, low-level researcher contact) nature of the intervention, a DSMC will be established and will meet quarterly to ensure safety of the participants and integrity and efficacy of the trial. Members will include clinical experts in stroke and an independent statistician, with an independent Chair appointed. Significant reporting of SAEs will be notified to the Trial Steering Committee of the findings who will discuss the issues arising and determine the action to be taken. A formal DMC charter outlining the remit and role of the DMC and the details of stopping rules for the trial will be drawn before the study commences and will be signed off by the DMC before the trial (Appendix B).

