## 40. APPENDIX C CASE RECORD FORMS

### List of TIIPS study case record forms

	Form Name	Purpose
1	Form A NHI number	Confidential record of NHI number
2	Form B Baseline and Screening	Screening for eligibility, and Baseline demographic and health related information
3	Form C Contact Details	Record of participant contact details, alternate contact and GP contact
4	Form F Follow-up	Follow-up assessments at 3, 6, 9 and 12 months
5	Form R Randomisation	Completion of data entry for randomisation, and record of group allocation
6	Form S Serious adverse events	Record of stroke/TIA/MI recurrent events, death and hospitalisation
7	Form Z Coaching assessment and compliance	Record of coaching sessions, compliance, and assessment of coaching quality

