8.16. Depression Score (Sub Total)

(Advise the participant and study manager to contact GP if the score is equal to or more than 11.)

---

Depression warning

---

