**Section 17. Health Service Use (3, 6, 9 and 12 months)**

17.1. Have you visited your GP since your stroke/TIA  Yes  No

17.1.1. If Yes, how often since your TIA/stroke?  Once  
 Twice  
 Three times  
 Four times  
 More than 4 times  
 Can't remember

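### The follow-up and SAE forms do not fully match the protocol's own event definitions: Form F has no question on admission, stroke or MI, and Form S has no mood field and no dated heart failure entry

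*Protocol*

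**What the plan says.** The Data Safety Management Committee section gives five categories of event for committee review: "SAEs will include all hospitalisation, new stroke, heart attack, death, and significant mood issues". The Serious Adverse Events section, which tells the research assistant when to complete Form S, names one: "All hospitalisations (for any reason) are classified as Serious Adverse Events (SAEs"). It then treats anything that does not meet the criteria for serious as non-serious, without listing those criteria.

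The secondary outcomes in section 11 include "CVD adverse outcomes (fatal and nonfatal stroke, TIA, myocardial infarction and heart failure, death attributable to CVD and all-cause mortality"). For this outcome the inferential analyses section says "we will use Kaplan-Meier life-test and estimate the hazard ratios (HR) and adjusted HR using time-to-event Cox regression analysis", and it extends the time-to-event analysis to recurrent events. Section 31 also makes adverse events, including hospitalisations, a secondary end point.

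Table 1 in section 20 lists, at baseline and follow-up, "CVD outcomes, recurrent events, hospitalisation (stroke, CVD events) self-report and/or from clinical records".

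Appendix C describes Form S as "Record of stroke/TIA/MI recurrent events, death and hospitalisation". Form F is the follow-up form for 3, 6, 9 and 12 months. Its health service section opens with "17.1. Have you visited your GP since your stroke/TIA" and continues with other services, home help, employment and private care. For each HADS subscore, Form F instructs: "Advise the participant and study manager to contact GP if the score is equal to or more than 11".

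**The concern.** A protocol can define events well and still lose them if the forms do not ask for them. Here the definitions, the source stated in Table 1 and the form fields do not line up at three points: how an event is first elicited at follow-up, where a mood SAE is recorded, and how heart failure gets a date.

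What is at stake is the completeness of what the data safety committee reviews and of one secondary outcome. An event treated without admission, if nobody asks about it at the time, may not be recoverable later from records. Mood deserves attention because the protocol itself lists it as a serious event for a psychological behaviour-change intervention.

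**Working it through.** No sample size, power or error rate is involved, so the check sets the definitions beside the form items and counts coverage. A few pieces of the forms were not in the text available: two near the start of Form F, and the part of Form S before its Section 3. Every statement of absence below is for the text shown.

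**Step 1. SAE categories against Form S**

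| SAE category | Form S item |
|---|---|
| Hospitalisation | 3.1 to 3.4: dates and ICD reason |
| New stroke | 4.3, dated at 4.3.1 |
| Heart attack | 4.5, dated at 4.5.1 |
| Death | 5.1 to 5.6: date, causes, ICD codes |
| Mood | none; visible only through the ICD code of an admission |

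Dedicated items: 1 + 1 + 1 + 1 + 0 = 4 of 5.

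**Step 2. CVD outcome components against dated Form S entries**

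| Component | Dated entry |
|---|---|
| Stroke | 4.3.1 |
| TIA | 4.4.1 |
| MI | 4.5.1 |
| CVD death | 5.2, with the cause coded at 5.4 |
| Death from any cause | 5.2 |
| Heart failure | none of its own; only the ICD code of an admission (3.3) or of a death (5.4) |

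Dated entries: 5 of 6. Outside Form S, heart failure appears as a tick box in Form F item 9.1, with no date field. Kaplan-Meier and Cox analyses need a date.

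**Step 3. Event questions on Form F**

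- Hospital admission: none. Section 17 does not ask about it.
- New stroke: none. The list in item 9.1 has no stroke entry.
- MI: none. Item 9.1 has coronary disease and angina but not MI.

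Event questions present: 0 of 3.

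TIA is listed in 9.1 and dated in 9.1.1. However, 9.1 says that an item ticked once is not displayed later. The primary aim admits people with recurrent TIA, so some will enter with that box already ticked and will not be prompted about a further TIA. The same display rule applies to the heart failure box.

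**Step 4. The mood route**

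Form F collects HADS at follow-up. Items 8.15 and 8.16 send a subscore of 11 or more to the GP and the study manager, and 8.17 records that a mental health form was sent and uploaded. No step leads from there to Form S. The protocol does not say what makes a mood issue significant, or whether the HADS flag is meant to identify it.

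**Step 5. Size**

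The documents give no rate for non-admitted heart failure, non-admitted mood crises, or events missing from records. The number of lost events cannot be calculated, and the coverage counts above are the only supportable measure.

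**The case against.** The case against is substantial, and most of it limits the point rather than removing it.

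- **Form S is not inadequate overall.** It covers four of the five SAE categories with dates, and answering no to admission sends the user on to the stroke, TIA, MI and death items. A death at home can be recorded. This stands.
- **The two SAE sections need not contradict each other.** Saying that all hospitalisations are serious does not say that only hospitalisations are, and the list follows in a later section. This stands. What remains is that the section triggering Form S gives no list and should be aligned with the one that does.
- **Self-report is not the only source.** Table 1 allows clinical records, and Form S lists national data, medical records and death certificates as sources for deaths. A reader might infer that events surface only if volunteered; the documents do not support that. But records are weakest for exactly the non-admitted events at issue.
- **Mood is not invisible.** HADS is measured at follow-up, the flag reaches the study manager, who also receives SAE reports, and the draft charter gives the committee secondary endpoints by group. A reader might infer that mood never reaches the committee; that goes too far. The missing piece is a route for mood as an SAE.
- **A first tick for heart failure at a follow-up places onset between two visits.** True, but the planned analysis makes no provision for interval-dated events.
- **Training and a Manual of Procedures, not shown, may contain prompts.** Possible, and it cannot be ruled out.

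A reader might also infer detection bias by arm. The coaching arm has 12 sessions, about 6 monthly calls and 4 assessments, 12 + 6 + 4 = about 22 contacts, against 4 in usual care. The documents do not establish such a bias: SAE reporting belongs to the research assistant, who is blinded and has the same four assessments in both arms, and coaches have no reporting role.

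Nor can the background figure of up to 25% adverse outcomes within 90 days serve as the trial's event rate. It comes from population-based studies of patients after TIA or minor stroke, and baseline may fall up to 6 weeks (42 days) after the index event, so part of that window can precede randomisation.

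**Conclusion.** The point holds in limited form. Form S is sound for admission, stroke, TIA, MI and death. The forms as shown fall short of the protocol's own definitions in three respects: none of the three main event questions is on Form F, one of five SAE categories (mood) has no Form S field and no criterion, and one of six CVD components (heart failure) has no dated entry unless it led to admission or death.

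The consequence is a risk, not a demonstrated loss: events managed without admission, and events not found in records, may be under-recorded. It touches committee review and secondary outcomes. The primary systolic blood pressure endpoint is unaffected. This should be fixed, preferably before recruitment, but it does not threaten the trial's main conclusion.

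The verdict assumes that the unseen parts of Forms F and S contain no event questions, and that no manual supplies an equivalent prompt.

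**What to change.** 1. Add to Form F, worded identically for both arms at 3, 6, 9 and 12 months, a question on any hospital admission, stroke or TIA, heart attack or heart failure since the last assessment. Any yes opens Form S. Table 1 has no 9-month column, so its event row should be extended to match.
2. Add to Form S a dated heart failure item and a mood SAE item.
3. Reconcile the Serious Adverse Events section with the list in the Data Safety Management Committee section. The sponsor should state what counts as a significant mood issue and how the existing HADS flag relates to it. The protocol does not equate a score of 11 or more with an SAE, so that threshold should not be adopted by default.
4. Base the between-arm comparison of events on these scheduled questions plus the same record check in both arms.

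The cost is a few REDCap items, aligned wording, about a minute per assessment and somewhat more SAE forms.
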